Table 8: The total sample size required to achieve different powers under different assumptions about the benefit of nitazoxanide (Delta) using a two-sided .05 level test	48

List of Figures

Figure 1: Average (+ SD) tizoxanide plasma concentration vs. time profiles by dose group	12
---	-----------

PROTOCOL SUMMARY

Full Title: A Randomized Double-Blind Phase 2 Study Comparing the Efficacy, Safety, and Tolerability of Nitazoxanide Versus Placebo in Addition to Standard Care for the Treatment of Hospitalized Subjects with Severe Acute Respiratory Illness

Short Title: NTZ-SARI

Clinical Phase: 2

IND Sponsor: Office of Clinical Research Policy and Regulatory Operations (OCRPRO)
National Institute of Allergy and Infectious Diseases (NIAID)

Conducted by: Mexican Emerging Infectious Diseases Clinical Research Network (LaRed)

Sample Size: N= 290 subjects

Accrual Ceiling: Up to 500 subjects will be screened to randomize 290 subjects

Study Population: Subjects who are hospitalized in Mexico with Severe Acute Respiratory Illness [SARI] (using the World Health Organization [WHO] case definition)

Accrual Period: 3 years

Background: Respiratory viruses are a significant cause of hospitalization for respiratory tract infections. Etiologic agents include influenza, parainfluenza virus, rhinovirus, adenovirus, metapneumovirus, respiratory syncytial virus (RSV), bocavirus and coronavirus. Of these, only influenza has a licensed treatment. Nitazoxanide (NTZ) is a licensed anti-infective agent with activity against many of these respiratory viruses. In a pediatric Phase 2 study of outpatient ILI, the NTZ cohort showed symptom resolution in 4 days versus 7 days in the placebo group. In a 624 person Phase 3 study of ILI, the NTZ cohort showed symptom resolution in 94 h compared to 108 h in the placebo group (p=0.0026). These benefits were observed in the entire cohort, not just those infected with influenza. If similar efficacy can be seen in the inpatient ILI population, there could be reductions in duration of hospitalization, morbidity, and costs.

LaRed is a collaboration between the Mexican Ministry of Health and the US NIAID. In a period of 4 years, LaRed has enrolled over 5600 subjects (of which over 2000 were hospitalized) into an observational ILI study at 6 sites in Mexico. Viral etiologies are found in approximately 60% of subjects enrolled.

Study Design: The study will be a multicenter, randomized, double-blind, placebo controlled trial to evaluate the efficacy of NTZ + standard of care (SOC) compared to placebo (PCB) + SOC in treating acute viral respiratory infections in adults and children \geq 12 months old with SARI (hospitalized ILI). It is anticipated that SOC would likely include antibiotics and may include treatment for influenza. The study is designed to enroll a total of 290 subjects who will be randomized in a 1:1 ratio. Subjects will be followed on Days 3, 7, 14, and 28. The subject will

be discharged from the hospital when clinically indicated as determined by the treating physician. Follow-up visits may occur as inpatients or as outpatients. Subjects still hospitalized on Day 28 will be followed until discharged from the hospital.

Study Duration:

Enrollment start date: February 2014
Anticipated enrollment end date: March 2017
Anticipated final analysis: December 2017

Study Agent: Nitazoxanide

Primary Objective: Evaluate the effect of NTZ in addition to SOC as compared to PCB + SOC in the treatment of SARI as measured by the time to hospital discharge

Secondary Objectives:

1. Evaluate the clinical efficacy of NTZ + SOC vs. PCB + SOC with regards to:
 - Percent hospitalized at Study Day 3, 7, 14 and 28
 - Death by Study Day 28
 - Duration of clinical symptoms (defined in Section 7.3.1.2)
 - Duration of fever
 - Use of supplemental oxygen (or increase greater than baseline oxygen requirement)
 - Admission to ICU
 - Intubation/mechanical ventilation
 - Proportion of subjects who develop complications including pneumonia, respiratory failure requiring mechanical ventilation, acute respiratory distress syndrome (ARDS), sepsis, or bronchiolitis.
 - Time to resumption of normal activity
 - Antibiotic/antiviral use during hospitalization
 - Systemic corticosteroid use during hospitalization
 - Re-hospitalization within 28 days
2. Evaluate the virologic efficacy of NTZ + SOC vs. PCB + SOC with regards to:
 - Percent cessation of viral shedding at Study Day 3
3. Evaluate the safety and tolerability of NTZ assessed by:
 - Cumulative incidence and severity of adverse events (AEs)
 - Cumulative incidence of serious AEs (SAEs)
 - Cumulative incidence of laboratory abnormalities on Study Days 3, 7 and 28

Endpoints:

Clinical Endpoints:

- Hospitalization on Study Days 3, 7, 14, and 28
- Date and time of hospital discharge
- Date of death, if applicable

- Clinical symptoms (measured daily through Study Day 14 and then again on Study Day 28)
- Temperature (measured daily through Study Day 14 and then again on Study Day 28)
- Oxygen use
- Date of admission to ICU and discharge from ICU, if applicable
- Date of intubation/extubation, if applicable
- Presence of complications during study (pneumonia, respiratory failure requiring mechanical ventilation, ARDS, sepsis, or bronchiolitis)
- Global assessment (measured daily through Study Day 14 and then again on Study Day 28) (defined in Section 7.3.1.3)
- Antibiotic/antiviral use during hospitalization (number and duration)
- Re-hospitalization within 28 days
- Use of systemic corticosteroids

Virologic Endpoints:

- Presence of virus on nasopharyngeal (NP) swab (or aspirate) at Study Day 3 (same virus as Day 0)

Safety Endpoints:

- AEs
- SAEs
- Chemistry and hematologic laboratory assessments on Study Days 3, 7 and 28

1 BACKGROUND INFORMATION AND SCIENTIFIC RATIONALE

1.1 Background

1.1.1 Burden of Influenza-Like Illness

Respiratory viral infections (RVI) are one of the most common health conditions in the world and have enormous but under-recognized impacts on public health. According to the World Health Organization (WHO) estimates, 450 million cases of pneumonia are recorded every year¹. In addition to their high frequency, RVIs are major causes of severe acute respiratory tract infection (SARI) that can lead to severe outcomes including hospitalization and death. Evidence of viral infection have been detected in 22% of cases in adults,¹⁻⁶ and 49% (range 43–67) of cases in children^{1,7-11}. Etiologic agents of influenza-like illness (ILI) include several respiratory viruses, such as influenza virus, parainfluenza virus, rhinovirus, adenovirus, metapneumovirus, respiratory syncytial virus (RSV), bocavirus and coronavirus¹².

Acute respiratory illnesses (ARIs) impose an enormous burden on communities both directly in terms of medical care and indirectly on the whole of society. Besides causing severe complications for patients, ARIs have huge impacts on outpatient care and hospital services, resulting in high costs for patients, families and society in general. In addition to direct costs of care, ARIs are responsible each year for major losses in productivity in part due to absenteeism.

1.1.2 Existing Treatments

Of the viruses causing ILI, only influenza has an effective treatment. Four medications are licensed for the treatment of influenza: oseltamivir (OST), zanamivir, amantadine, and rimantadine. Parainfluenza virus, rhinovirus, adenovirus, metapneumovirus, respiratory syncytial virus (RSV), bocavirus and coronavirus have no effective therapy.

1.1.3 WHO's Battle Against Respiratory Viruses (BRaVe) Initiative

In July and November 2012 the World Health Organization (WHO) held 2 informal consultations to introduce a new initiative. “Battle against respiratory viruses” (BRaVe) is highlighting the need of effective treatment options for non-influenza respiratory viruses. From these consultations, the WHO released a Call to Action, specifically stating “cost-effective antiviral agents and other therapies for other (non-influenza) VRIs are not currently available, and an urgent need exists to support research for new safe and effective therapeutics to target specific respiratory viruses but also, if possible, to develop antivirals with broad spectrum activity.”

1.1.4 Severe Acute Respiratory Illness

The WHO has created a case definition for SARI. This case definition was created for outbreaks such as severe acute respiratory syndrome (SARS) and pandemic influenza.

The WHO 2004 SARI case definition was:

Meets ILI case definition (sudden onset of fever $\geq 38^{\circ}\text{C}$ and cough or sore throat in the absence of other diagnosis) AND shortness of breath or difficulty breathing AND requiring hospital admission.

The WHO²² SARI case definition was revised in 2014 to read:

An acute respiratory infection with:

- history of fever or measured fever of $\geq 38^{\circ}\text{C}$;
- and cough;
- with onset within the last 10 days;
- and requires hospitalization.

This case definition is the basis for defining a severe respiratory illness in the selection of participants in this protocol.

1.2 Nitazoxanide

1.2.1 History and Significance

Nitazoxanide (NTZ) is an investigational new drug for the treatment of acute influenza that has also demonstrated efficacy against other respiratory illnesses. NTZ is the approved generic name for 2-acetyloxy-N-(5-nitro-2-thiazolyl)-benzamide, also known as PH-5776, or Alinia®. The drug is already marketed in the United States as an oral suspension for children ≥ 1 year of age and as tablets for patients ≥ 12 years for treatment of *Giardia lamblia* or *Cryptosporidium parvum*. In Mexico, NTZ is licensed for use in patients ≥ 2 years of age.

1.2.2 Mechanism of Action and Pre-Clinical Findings

Anti-influenza activity of NTZ and its circulating metabolite, tizoxanide, has been demonstrated in several human and canine cell lines after infection with 4 different strains of influenza A virus (including 2 mammalian H1N1 strains, 1 H3N2 strain, and the H5N9 low pathogenicity avian strain) and 1 strain of influenza B virus with EC50s between 0.3 and 1 $\mu\text{g/mL}$.

In cell culture, tizoxanide has antiviral activity against other RNA and DNA viruses. It inhibits replication of parainfluenza (Sendai virus, IC50 = 1 $\mu\text{g/mL}$), coronavirus (canine strain S-378, IC50 = 1 $\mu\text{g/mL}$), adenovirus type 5, and respiratory syncytial virus A2 [REDACTED]. Rhinovirus is not thought to be inhibited by NTZ.

The wide spectrum of antiviral activity suggests a cell-mediated effect rather than a specific viral target. Tizoxanide inhibits the replication of H1N1 and other strains of influenza A virus by a novel mechanism, acting at the post-translational level by selectively blocking the maturation of the viral hemagglutinin at a stage preceding resistance to endoglycosidase H digestion, thus impairing hemagglutinin intracellular trafficking and insertion into the host plasma membrane, a key step for correct assembly and exit of the virus from the host cell.¹³

The antiviral activity of NTZ alone or in combination with the neuraminidase inhibitors, OST phosphate and zanamivir, was studied in MDCK cells infected with 2 different strains of influenza A virus. NTZ exhibited synergism when combined with OST or zanamivir during

[figure not shown]
infections with the H1N1 A/PR/8/34 (PR8) influenza A strain. NTZ also exhibited synergism when combined with OST during infections with the avian A/Ck/Italy/9097/97 (A/Ck) influenza A strain. No cell toxicity was detected at the highest doses in the combination studies in uninfected cells.

1.2.3 Pharmacokinetics of Nitazoxanide and Tizoxanide in Humans

NTZ is not detectable in the plasma following oral administration of the drug. The main metabolites of NTZ in man are tizoxanide and tizoxanide glucuronide. Tizoxanide is highly bound to plasma proteins (>99%). The absorption of NTZ in immediate release tablets is significantly enhanced (Cmax and AUC of tizoxanide and tizoxanide glucuronide in plasma are almost doubled) when it is administered with food. In fasted human volunteers receiving a single 500 mg dose of ¹⁴C-NTZ, approximately one-third of the dose was excreted in urine as tizoxanide and tizoxanide glucuronide, and two-thirds was excreted in feces as tizoxanide. No other significant metabolites were detected [REDACTED].

During a Phase 2b/3 clinical trial for treatment of acute uncomplicated influenza, pharmacokinetics was studied in 6 subjects after receiving 300 mg NTZ with food and 10 subjects after receiving 600 mg NTZ with food. The study medication was administered twice daily for 5 days, and the blood samples for pharmacokinetics were collected over a 12-hour period [REDACTED]

A large black rectangular area, likely a placeholder or a redacted section of a document. It is positioned on the left side of the page, occupying most of the vertical space. The right side of the page is white, and there is a thin black border around the entire image.

1.2.4 Phase 2 Clinical Trials of NTZ in Subjects with Viral Respiratory Infection

In children age 1-11 years, 100 subjects (50 NTZ/50 placebo [PCB]) with viral respiratory infection for less than 72 hours duration were included and given an age-based dose of NTZ 100-200 mg twice daily (BID) or PCB for 5 days. Criteria for respiratory infection were met by fever, at least 1 respiratory symptom (cough, nasal discharge or congestion, sneezing, or sore throat), and at least 1 constitutional symptom (myalgia, malaise, fatigue, headache, chills/sweat). The NTZ cohort showed symptom resolution in 4 days (median, IQR 2-7) versus >7 days (median, IQR3->7) in the placebo group ($p<0.0001$, log rank test). Furthermore, analysis of secondary endpoints showed that the pediatric patients randomized to placebo were more likely to experience at least 1 illness-related physical exam abnormality at Day 7 follow up (81% vs. 28%, $p<0.0001$) and that they were also more likely to require post-study antibiotics (64% vs. 9%, $p<0.0001$). Lastly, treatment with NTZ was associated with a significant decline in the amount of nasal discharge (as measured by daily weighing of used facial tissues) during the 5-day treatment period ($p=0.0347$).

Using the same design and endpoints as the pediatric Phase 2 study, a second Phase 2 study was conducted in adults and adolescents (age ≥ 12 years). There were 86 subjects included (43 NTZ/43 PCB) with viral respiratory infection. Subjects were randomized to either NTZ 500 mg BID or PCB for 5 days. Time to resolution of symptoms was a median of 4 days (IQR >3-5) in the treatment arm versus 7 days (IQR 3->7) in the placebo group ($p=0.0365$, log rank test). Secondary efficacy analysis also showed that patients randomized to the placebo treatment group were more likely to have at least 1 illness-related physical exam abnormality on Day 7 follow up (71% vs. 37%, $p=0.0032$). At Day 7 follow-up, the placebo group was twice as likely to require antibiotics (36% vs. 18%), but this finding was not statistically significant ($p=0.132$). The mean weight of tissue collected over the treatment period was also higher for patients in the placebo group, but this was also a statistically insignificant result ($p=0.20$).

1.2.5 Phase 2b-3 Clinical Trial of NTZ in Acute Uncomplicated Influenza

During the 2010-2011 flu season, a Phase 2b-3 trial in 74 outpatient centers enrolled 624 subjects between the ages of 12 and 65 years who presented with acute uncomplicated influenza (symptoms onset <48 h).²³ At baseline, 41% of patients had confirmed (RT-PCR) influenza infection (50% AH1N1, 30% Influenza B, 20% AH3N2). Rhinovirus was the second-most detected pathogen (14%) of enrolled patients, followed by coronavirus (3%). Over one third of patients (37%) had no pathogen detected by RT-PCR.

Randomized subjects were given the extended release formula of NTZ 600 mg BID for 5 days. In a population infected with influenza, NTZ reduced time from illness onset to alleviation of flu symptoms (95.5 h in 600 mg dose [IQR 71-126] and 116.7 h in PCB [IQR 91-144] respectively, p=0.0084). The median duration of symptoms for the 300 mg cohort (109.1 h in 300 mg dose [IQR 82-152]) was not statistically more significant than placebo (p=0.5208).

Analysis of all patients treated (i.e., all ILI, not just those with influenza) also showed a statistically significant reduction of times from first dose to resolution of symptoms for the 600 mg NTZ treatment group (median 94.9 h, IQR: 62-126) compared to the placebo group (median 108.2 h, IQR: 82-152, p=0.0026).

An analysis of the subset of 37% of subjects with no virus identified at baseline also showed a dose-dependent reduction in duration of symptoms with a statistically significant difference (p=0.0208) observed between the 600 mg NTZ treatment group (median 88.4 h, IQR: 60-120) and the placebo group (median 105.7 h, IQR: 76.5-160). The numbers of subjects with other laboratory-documented respiratory virus infections at baseline were too small to draw meaningful interpretations, although the data suggested that there was no apparent treatment effect in subjects infected with rhinovirus.

There are no data on the use of NTZ in a hospitalized population with influenza or other causes of ILI.

1.3 Etiology and Burden of ILIs in Mexico

During 2009-2010, a new influenza virus (A/California/07/2009 H1N1) spread worldwide causing the first flu pandemic in more than 40 years. Because of the significant fatality rates and the fact that Mexico City was the epicenter of the earliest reported cases, the Mexican Ministry of Health and NIAID collaborated to establish the LaRed network. LaRed's observational cohort study of ILIs in Mexican adults and children has over 5600 subjects over 4 years (data as of July 2014). Analysis of the first years data found that, in addition to influenza which accounted for 24% of viral isolates, rhinovirus, coronavirus, RSV, and adenovirus contributed significantly to the burden of disease, accounting for 25%, 14%, 10%, and 9% of all viral isolates respectively.¹² Similar results are seen in the 3 year data (unpublished). For severe (hospitalized) disease, similar viruses caused disease (see Table 2). While NTZ is not thought to treat rhinovirus, it is thought to be efficacious in treating adenovirus, coronavirus, influenza, parainfluenza, and RSV, and likely efficacious in treating mixed infections. Additionally, in the Phase 2b-3 data there was efficacy in the “negatives” (pointing to likely infectious agent). Taken together, these categories make up 76% of hospitalized ILI (i.e., SARI) patients that LaRed has been able to enroll previously.

Table 2: Pathogen distribution in hospitalized ILI cases in LaRed over 3 years, by age group

Pathogen	Children ≥ 2 to <12 years old	Adults ≥ 12 years old	Total	%Total
Adenovirus	6	24	30	2.2
Bordetella pertussis	2	5	7	0.5
Coronavirus	9	55	64	4.7
Coronavirus 229E	2	18	20	
Coronavirus NL63	3	20	23	
Coronavirus OC43	4	17	21	
Chlamydophila pneumoniae	0	0	0	0.0
Influenza	21	112	133	9.7
Influenza A	2	10	12	
Influenza A H1N1	7	34	41	
Influenza A H3N2	5	44	49	
Influenza B	7	24	31	
Legionella pneumophila	0	0	0	0.0
Metapneumovirus	17	34	51	3.7
Mycoplasma pneumoniae	2	18	20	1.5
Parainfluenza	15	29	44	3.2
Parainfluenza 1	4	2	6	
Parainfluenza 2	5	8	13	
Parainfluenza 3	4	9	13	
Parainfluenza 4	2	10	12	
Rhinovirus	40	207	247	18.0
RSV	44	35	79	5.7
RSV A	37	31	68	
RSV B	7	4	11	
Mixed	43	107	150	10.9
Negative	54	497	551	40.0
Total	253	1,123	1,376	

Given the potential efficacy in influenza and other respiratory viruses as described above (section 1.2.4 and 1.2.5), the hospitalizations and morbidity associated with these viruses described in this section, and the lack of data of NTZ in this hospitalized SARI population, LaRed would like to study the use of NTZ for the treatment of hospitalized subjects with SARI.

1.4 Risks and Benefits

1.4.1 Risks of NTZ

NTZ has been marketed in the United States since 2003 and in Latin America since 1996. It is estimated that more than 50 million patients have been exposed to NTZ post-marketing worldwide. No drug-related serious adverse events (SAEs) have been reported during post-marketing experience with NTZ.

Phase 2 and 3 clinical studies have been conducted in approximately 4,000 patients to evaluate the safety and efficacy of NTZ in treating parasitic, bacterial, and viral infections. During these studies, no drug-related SAEs were observed. The side effects have been usually of a mild transient nature, and less than 1% of patients have discontinued therapy because of an AE. The most common AEs reported in clinical trials include abdominal pain, diarrhea, headache, nausea, and vomiting and did not differ significantly from those of placebo. Clinical chemistry and hematology obtained before and after treatment have not revealed any abnormalities attributable to the test drug.

Nitazoxanide is US FDA Pregnancy Category B: No impaired fertility or harm to the fetus in animal studies was noted, but there are no adequate and well-controlled studies in pregnant women.

1.4.2 Risk of Phlebotomy

The primary risks of phlebotomy include local discomfort, occasional bleeding or bruising of the skin at the site of needle puncture, and rarely hematoma, infection, or fainting. At the time of enrollment and during study visits, each subject will be asked about participation in other research studies to ensure that blood draws do not exceed each institution's limits of blood drawn.

In children, the volume of blood samples for this study required for each visit represents 0.4% of circulating blood volume in well-nourished children, up to 1% of the circulating volume in malnourished children. Therefore, on a month-long study, the total volume of blood required is 1.2% to 3% of circulating blood volume, depending on the constitution of each child.

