3.4 Overview of Study Design

The study will be a multicenter, randomized, double-blind, placebo controlled trial to evaluate the efficacy of NTZ+ SOC compared to PCB + SOC in treating acute viral respiratory infections in adults and children \geq 12 months old with SARI. The study will be conducted in up to 8 sites within Mexico, at sites that are part of the LaRed network. Subjects will be selected according to the inclusion and exclusion criteria listed below (Sections 4.3 and 4.4). The study is designed to enroll a total of 290 subjects who will be randomized in a 1:1 ratio. Enrollment will continue until 290 subjects are randomized, or March 2017, whichever comes first.

Prior to screening for inclusion in the study, informed consent (and assent for pediatric subjects as applicable) will be obtained. After completion of informed consent, screening for the study will occur. This involves review of the subjects' symptoms, medical conditions, physical exam, and pregnancy test for females able to become pregnant. All patients will initially be hospitalized. If the subject qualifies for the study, baseline assessments will occur including baseline vitals, safety labs, and nasopharyngeal swab or aspirate for PCR. Subjects will be randomized to a treatment kit and will begin treatment immediately. They will receive instruction on completion of their diaries, concomitant medications, and attending follow-up visits. Subjects will be followed on Study Days 3, 7, 14, and 28. The subject will be discharged from the hospital when clinically indicated as determined by the treating physician – follow-up visits may occur as inpatients or as outpatients.

On Study Days 3 (+/- 1) and 7 (+/- 1) a clinical assessment will be performed, diary cards collected, and safety labs will be obtained. Subjects that are hospitalized on Day 14 will have an in person visit. For subjects that are no longer hospitalized, the Day 14 visit may occur in person or by telephone. This visit is primarily for the collection of Day 7-14 diary card information. Study Day 28 will mark the end of study where subjects return for final clinical assessment, safety labs, and convalescent serologies.

Subjects that are still hospitalized after Study Day 28 will continue to be followed through the date of discharge.

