4.9 Participation in Other Protocols

Subjects in this protocol may participate in other research protocols, as long as the other research does not require more than 30 mL of blood to be given in any 4-week period of time and does not administer any unlicensed drug, unlicensed vaccine, or any treatment (licensed or unlicensed) for influenza or influenza like illness within the 30 days or 5 half-lives (whichever is longer) prior to enrollment or during the duration of this study.

LaRed has an ongoing ILI/SARI surveillance study and it is anticipated many subjects may be co-enrolled in this study.

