6.2.3.2 Laboratory Data

The following laboratory test will be performed:

- CBC with differential white cell count (to include neutrophil, lymphocyte, and eosinophil percentages), hemoglobin, hematocrit, and platelets
- Blood chemistries (creatinine, ALT/GPT, AST/GOT, total bilirubin, LDH, CRP)

If these labs were performed for clinical care on the day of enrollment (or within 24 hours prior to enrollment), these labs do not need to be repeated and can be obtained from the clinical record. These tests are performed as a baseline for safety monitoring, and results do not need to be obtained before starting study drug.

If laboratory tests are drawn after enrollment, within 24 hours of enrollment these labs should be reviewed. If laboratory results that show estimated CrCl < 30 mL/min, total bilirubin >2×ULN, or AST/ALT >3×ULN, the study drug should be stopped (per section 4.6)).

6.2.3.3 Research Procedures on Day 0

At baseline, a NP swab will be sent for multiplex PCR. If a NP swab cannot be obtained for medical reasons, an NP aspirate can be substituted. See Section 7.2

If this testing is performed for clinical care or other protocols on Day 0, and the results can be used for this study, the testing does not need to be repeated.

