7 MEASURES OF SAFETY, EFFICACY, AND COMPLIANCE

7.1 Safety Evaluations

7.1.1 Laboratory Evaluations

All laboratory evaluations (except reference endpoint assays) will be performed at the local certified (e.g., Clinical Laboratory Improvement Amendments [CLIA], College of American Pathologists [CAP], or comparable certification) clinical laboratory. The same laboratory should be used throughout the study for any given patient. Blood samples will be collected from subjects at baseline (Day 0) and on Study Days 3, 7, and 28 for evaluation of routine laboratory safety (chemistry, complete blood count with differential).

Abnormal labs, if thought to be erroneous, should be repeated. Not all abnormal labs need to be repeated. Abnormal labs, if thought to be erroneous, which will cause cessation of study medication, should be confirmed by repeating the lab test as soon as possible.

On the designated days, the following laboratory test will be performed:

- CBC with differential white cell count (to include neutrophil, lymphocyte, and eosinophil percentages), hemoglobin, hematocrit, and platelets
- Blood chemistries (creatinine, ALT/GPT, AST/GOT, total bilirubin, LDH, CRP)

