12 STORED SPECIMENS, AND DATA

12.1 Samples/Specimens

The samples collected during this study are for clinical laboratory and virologic (respifinder) testing only. No samples are stored as part of this protocol.

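### Section 1.4.2's paediatric blood total of 1.2% to 3% covers three draws, but the protocol schedules four, for a full-schedule maximum of 1.6% to 4%

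*Protocol*

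**What the plan says.** **Volume.** Protocol section 1.4.2 (Risk of Phlebotomy) says the blood volume "required for each visit represents 0.4% of circulating blood volume in well-nourished children", and "up to 1% of the circulating volume in malnourished children". From these it derives a study total: "the total volume of blood required is 1.2% to 3% of circulating blood volume, depending on the constitution of each child". It gives no count of draws.

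**Schedule.** Section 7.1.1 says "Blood samples will be collected from subjects at baseline (Day 0) and on Study Days 3, 7, and 28". Table 5 marks the haematology panel and the chemistry panel four times each. Sections 6.2.3.2, 6.2.4.2, 6.2.5.2 and 6.2.7.2 list the same blood count and chemistry panel for Days 0, 3, 7 and 28. The Day 14 visit has no laboratory tests.

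**Substitution.** Section 6.2.3.2 lets clinical results stand in for the baseline draw, in the sentence that begins "If these labs were performed for clinical care on the day of enrollment (or within 24 hours prior to enrollment), these labs do not need". The Day 3, Day 7 and Day 28 sections carry an equivalent allowance for tests done on the study day or within the window.

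**Serology.** The design overview in section 3.4 says that at Day 28 "subjects return for final clinical assessment, safety labs, and convalescent serologies". Section 12.1 says: "The samples collected during this study are for clinical laboratory and virologic (respifinder) testing only". It adds that nothing is stored.

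**The concern.** Section 1.4.2 reaches its total from a per-visit volume, so the total should equal that volume times the number of visits with blood sampling. It equals three visits' worth, and the protocol has four. The understated figure is the only place where the protocol gives the trial's own blood burden on children. It stands in the same section that tells sites to ask about other research so that draws stay within institutional limits. A site or ethics committee that wants to know what this trial contributes would read a number that is too low for a child who has every scheduled draw.

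The serology phrase is a separate inconsistency. A site working from the section 3.4 overview could draw a Day 28 sample that no endpoint and no SAP analysis uses.

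**Working it through.** **Inputs from the protocol**

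- Per-visit volume (section 1.4.2): 0.4% for well-nourished children; up to 1% for malnourished children.
- Stated study total (section 1.4.2): 1.2% to 3%.
- Scheduled draws (section 7.1.1, Table 5, the four visit sections): Days 0, 3, 7 and 28, so 4.

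**Formula:** total = per-visit volume × number of study draws.

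**Reproducing the stated figure.** The implied number of draws is 1.2 / 0.4 = 3 at the lower end and 3 / 1 = 3 at the upper end. Both ends agree, and no other count matches.

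| Study draws | Well-nourished | Malnourished (up to) |
|---|---|---|
| 1 | 0.4% | 1% |
| 2 | 0.8% | 2% |
| 3 (matches section 1.4.2) | 1.2% | 3% |
| 4 (full schedule) | 1.6% | 4% |

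**Size of the gap**

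- Absolute: 1.6 − 1.2 = 0.4 percentage points; 4 − 3 = 1 percentage point.
- Stated total relative to the full schedule: 1 − 1.2/1.6 = 25% too low (the same from 1 − 3/4).
- Full schedule relative to the stated total: 1.6/1.2 − 1 = one third higher.

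**Where the three may come from.** The safety endpoints in section 3.6.2 list laboratory assessments on Days 3, 7 and 28 only, which is three. A count taken from that list would omit the baseline draw. The documents do not confirm this.

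**Serology.** No arithmetic is possible, because section 3.4 gives no volume. Side by side:

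- Section 3.4 has convalescent serologies at Day 28.
- Table 5, section 6.2.7.2 and section 7.1.1 list no serology.
- Section 6.2.3.2 lists no acute-phase serum on Day 0 to pair with a convalescent one.
- Section 12.1 limits samples to clinical laboratory and virologic testing.
- The endpoints in section 3.6.2 and the SAP's secondary analyses contain no serological outcome.

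**The case against.** The strongest defence is the substitution rule. All children are in hospital at baseline, so a clinical blood count and chemistry within the 24-hour window are plausible. One substitution leaves three study draws, which is the stated 1.2% to 3%, and two or more leave less. This defence stands in part: 1.6% to 4% is a ceiling, and a reader who inferred that every child gives that much would be going beyond the documents. The 1% is itself an upper figure.

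The defence does not rescue the stated total. Substitution is conditional, it applies equally at all four visits, and section 1.4.2 does not mention it, so nothing fixes the count at three. The documents give no substitution rate. Clinical results are also less likely to be available at Day 28: the stays used for the sample size in section 9.2 averaged 7.7 days, and the truncation there removed only about 4% of the data.

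Three stronger readings are tempting but not supported:

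- **That the case for including children rests on this total.** Sections 4.1.1 and 4.1.2 argue from licensing, earlier paediatric use and disease burden. The institutional-limit check in section 1.4.2 works by asking about other studies and does not refer to the percentage.
- **That serology makes the burden higher still.** No volume is given, and every operative section leaves serology out, so it looks like leftover wording.
- **That the co-enrolment rule permits a much larger combined loss.** Section 4.9 admits other research that "does not require more than 30 mL of blood to be given in any 4-week period of time", with no scaling to body size. Turning that into a percentage needs body weights and blood volumes per kilogram that the documents do not give. It would also ignore the institutional limits that section 1.4.2 applies in addition. Rewriting section 4.9 would be a preference and would not correct an error.

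**Conclusion.** Wrong as written, minor severity. At the protocol's own per-visit volumes, the full schedule of four draws takes 1.6% (well-nourished) to 4% (malnourished) of circulating blood volume, against the stated 1.2% to 3%. The stated total is a quarter below the full-schedule maximum. The result rests on two things: that the per-visit figures in section 1.4.2 are correct, and that no draw is replaced by clinical-care results. Where one draw is replaced, the stated total holds, and where more are replaced it is too high. That section 1.4.2 counted three draws is inferred from the arithmetic, although both ends of the range agree.

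The serology phrase in section 3.4 contradicts the rest of the protocol but adds nothing that can be quantified. The statistical design is not affected by either item.

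**What to change.** 1. In section 1.4.2, state the total as up to 1.6% (well-nourished) to 4% (malnourished) for four draws, on Days 0, 3, 7 and 28, and note that use of clinical-care results at any visit reduces it. Make the same change in any consent or assent text that repeats the figure.
2. In section 3.4, delete the mention of convalescent serologies, so that the overview agrees with Table 5 and sections 6.2.7.2, 7.1.1 and 12.1.

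The cost is two wording changes and a slightly less favourable stated burden. No planned analysis is lost, and the sampling schedule, endpoints and sample size stay as they are. Section 4.9 needs no change on this account.
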